5.5 Preparation of Sodium Nitrite Cream and Placebo

Sodium nitrite cream for use in humans will be provided by Pine pharmaceuticals and dispensed by the local hospital pharmacy. A complete description of the sodium nitrite cream preparation and properties is in Section 10.

5.6 Quality of Life and VAS Scale

A quality of life assessment using ASCQ-me will be completed by the subject before initial cream application and at the end of study. The VAS scale will be administered at each patient encounter.

5.7 Tissue sampling - Skin Biopsy

A 3-4 mm punch biopsy of the ulcer edge will be performed with local anesthesia at the edge of one of the ulcers in patients with ulcers.

Biopsy material will be divided in two: a portion will be frozen, or immediately homogenized for further study; another portion will be fixed in 10% formalin and analyzed as follows. The skin biopsy will be fixed in 10% neutral buffered formalin and routinely processed and sectioned for histological examination by our collaborator [name], a pathologist at Montefiore Medical Center. Histological examination will focus on the assessment of dermal bloodvessels, dermal stromal cells (especially the fibroblasts), and inflammatory infiltrate. Immunohistochemistry will be performed to further characterize the skin biopsy: (1) for the assessment of vascular density, immunohistochemistry staining using antibodies to CD31 (endothelial cell marker), CD34 (endothelial cell marker), and SMA (vascular smooth muscle cell marker), (2) plasma cell infiltration by CD138 (plasma cell marker), and (3) the number of activated fibroblasts by Yes-associated protein (YAP) and phosphorylated YAP (pYAP). The number of vessels, CD138+ plasma cells, and YAP+ fibroblasts will be counted for 10 high power fields. Special stains for microorganisms will also be performed on the tissue sections to exclude the possibility of infection: PAS-D (fungal stain), GMS (fungal stain), AFB-FITE (acid fast bacteria), and B&H (bacteria).

Immunofluorescent staining, collagen formation, and microvessel density.

Five-micron-thick sections of formalin fixed scars will be stained with hematoxylin and eosin (H&E) and evaluated for the following parameters: epidermal and dermal regeneration, granulation tissue formation, presence or absence of edema, congestion, hemorrhage, thrombosis, and intravascular or intervascular fibrin formation. Thickness of granulation tissue and epidermal regeneration will be scored as previously described⁴³. Inhibition of lipid peroxidation restores impaired vascular endothelial growth factor expression and stimulates wound healing and angiogenesis⁴³.

6.1 Clinical and Laboratory Methods

Routine laboratory studies will be obtained in clinic prior to the initiation of therapy and during follow up visits as deemed necessary by the clinical team. They may include CBC with differential, reticulocyte count, basic metabolic panel, uric acid, hepatic panel, LDH, pro-BNP, hemoglobin electrophoresis, microalbuminuria, urinalysis, serum ferritin, erythropoietin, and G6PD status.

Methemoglobin analysis will be performed by the clinical lab.

Three 5-10 cc serum, EDTA, and sodium heparin samples will be stored for future testing. These tubes will be spun at 3000 RPM, and plasma, serum, RBC will be aliquoted into freezer vials. The freezer tubes used are Sarstedt No./REF 72.694.006 (clear) for the plasma, and Sarstedt No./REF 72.694.034 (brown) for the RBC. They are 2mL micro tubes. The tubes will be barcoded and placed in boxes in the -80 freezer.

A Pax gene and a saliva sample will be collected at baseline.

All samples will be sent to Einstein College of Medicine bio-repository facility.

6.2 Specimen Storage, Tracking and Disposition

INTENDED USE OF SAMPLES/SPECIMENS/DATA

Samples and data collected under this protocol may be used for future studies of biomarkers (for example, soluble cell adhesion molecule (CAM), nitric oxide consumption, amino acid levels, cytokines, chemokines, endothelin, nitrate/nitrite levels, and other biochemical markers that may indicate vascular dysfunction, cell proliferation or wound healing.). Stored plasma will be reviewed for applicable future biochemical marker assays that become available in the future.

23

PI: [name] Version 5 The coded results of clinical and research tests and samples obtained during participation in this study may be combined with other related research studies performed at Einstein College of Medicine. This will help to increase the amount we can learn from the information obtained and reduce the number of duplicate tests that are performed for research. Coded samples may also be sent to our collaborators for analysis after a MTA or other appropriate documentation is in place.

Sample, Specimen, and Data Storage

Access to research samples will be limited. The samples will be placed in the freezer. Samples and data will be stored using codes assigned by the investigators or their designee(s). Data will be kept in password-protected computers. Only investigators or their designee(s) will have access to the samples and data.

All samples stored will be barcoded for a complete inventory. Only investigators (or their designee(s)) will have access to the samples and data.

Sample, Specimen, and Data Tracking

Research samples acquired from all time points will be labeled and tracked utilizing the BSI II Barcoding system. All samples will be stored in a -80 freezer, off site, in a secured repository. They can only be accessed by approved users.

Samples, Specimens, and Data at Completion of Protocol

In the future, other investigators may wish to study these samples and/or data. In that case, IRB approval must be sought prior to any sharing of samples. Any clinical information shared about the sample with or without patient identifiers would similarly require prior IRB approval.

7.1 Monitoring of Subjects and Criteria for Withdrawalof Subjects

Monitoring: The safety of topical sodium nitrite will be closely monitored. Vital signs will be obtained before application and post-application at hours 1, 2, 3, 4, 5. If no decrease in systolic blood pressure is detected (clinically significant hypotension: see Section 7.1), patients will be discharged home.

The primary expected toxicity is low grade, asymptomatic methemoglobinemia. Therefore, a blood sample for methemoglobin safety measurement will be obtained after the first application, then weekly.

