- Apply 2 layer compression wrap to leg (depending on the condition of theulcer)
- Use of topical or systemic antimicrobials

All participants will be requested to complete the Brief Pain Inventory (BPI) prior to initiation of the therapeutic portion of the trial.

Baseline visit: The following tests will be performed:

- 1. Baseline labs, which include CBC, reticulocyte count, CRP, ESR, LDH, hepatic panel, basic metabolic panel, ferritin, Pro-B Natriuretic Peptide (BNP), urinalysis, urine microalbumin, uric acid, urine pregnancy test (female at reproductive age)
- 2. Research labs: Pax gene, and stored 5-10 cc blood samples
- 3. Saliva for DNA analysis
- 4. The surface area of ulcer(s) will be measured and photographed with defined lighting, distance, exposure and camera type
- 5. A pain assessment tool (VAS assessment)
- 6. Brief Pain Inventory (BPI), ASCQ-ME, PROMIS surveys, Beck Depression Inventory

Screening visit and baseline visits can be combined in one appointment.

After at least two weeks of "run in period", where the patient is treated with standard of care therapies only, the total ulcer surface will be measured and, if there isn't a reduction of>25%, the patient will be randomized to receive sodium nitrite cream or placebo.

A biopsy of the ulcer will be obtained in patients that consent during the run inperiod.

Week 1/Visit 3: First application of "study cream". After cleaning the wound, the wound will be measured by light photography and manually by wound nurse, a microbiome sample will be obtained, and the "study cream" will be applied to all the ulcerated surfaces. Vital signs will be obtained before application to establish baseline MAP and post-application at hours 1, 2, 3, 4, 5. If no significant decrease in MAP pressure from baseline is detected (clinically significant hypotension, or symptomatic dizziness, tachycardia, or hypoxia as per the judgment of the PI), the patient will be discharged and instructed to return for a second application two to three days later. Methemoglobin will be obtained one hour ± 30 min after creamapplication.

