Week 2-10/ Visits 4-22: The subjects will be seen twice a week for cream application, wound care and monitoring of side effects. The wound will be measured once a week manually by the wound care nurse and measured by photography after 10±2 applications. Blood pressure and vital signs will be measured upon arrival to outpatient unit and 30 minutes±10 minutes after the application of the study cream, unless clinically indicated. If the blood pressure is stable after cream application for all visit 4, 5, 6, post cream application blood pressure monitoring wound not be needed for future study visits. The wound will be cleaned and study cream will be applied.

Routine bloods will be drawn as clinically indicated. A research methemoglobin level will be obtained every other week.

A repeat pregnancy test will be performed at week 4 in women of reproductive age. Pain assessment: a VAS scale will be obtained with each application of the study cream. If there is more than one ulcer, individual VAS scale per ulcer will be obtained.

After the first three subjects have completed the first application of the study drug, if there are no significant side effects, especially significant changes in BP, patients will be offered the option of applying the second weekly dose of the cream at home, by themselves or by a home health nurse. We will dispense the exact amount of cream to be applied eachweek. This will reduce the number of visits to the wound care / hospital location to once a week.

End of study: Subjects will return the week after the last application to have the study cream removed and for end of study procedures. Blood pressure and vital signs will be measured with a pulse oximeter. The surface area of all ulcerated surfaces will be measured and photographed with defined lighting, distance, exposure, and camera. The wound doctor or nurse will remove the "study cream" and obtain a repeat microbiome sample. A VAS scale will be obtained to assess pain. If there is more than one ulcer, individual VAS scales will be obtained per ulcer. ASCQ-ME, PROMIS, BDI, and BPI surveys will be distributed to the patient. Study labs will be obtained (see Appendix 1). Patients who discontinue the study will still receive end of study procedures.

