Week on Study Intervention		Week ~-2	Week ~-1	Week 1	Week 2	Week 3	Week 4	Week 5	Week 6	Week 7	Week 8	Week 9	Week 10	Week
Assessment Window	-	-	-	± 3 d	± 3 d	± 3 d	± 3 d	± 3 d	± 3 d	± 3 d	± 3 d	± 3 d	± 3 d	± 3 d
Study Procedure		•						 						
Informed Consent	х													
Basic Contact Info	х													
Demographics	х													
Medical History	х													
Beck Depression Inventory		x												x
ASCQ-Me		x												x
PROMIS		x												x
Brief Pain Inventory		x	x											x
Concomitant Medications	х	x		xx	xx	xx	xx	xx	xx	хх	xx	xx	xx	x
Vital Signs	x	x	x	xx	xx	xx	xx	xx	xx	xx	xx	xx	хх	x
Baseline Physical Exam		x												
Non-Baseline Physical Examination	x			v3				x						x
MetHb	х			v3				x				x		
G6PD	χa													
Hb Electrophoresis	x ^b													x
Baseline and EOS Labs		х												x
Monitoring Labs				x				X				х		
Research Labs (3 tubes) Saliva for DNA		x												x
Analysis		x												
Urine Pregnancy Test*		x						x						x
Randomization				v3										
Application of Cream				xx	xx	xx	xx	xx	xx	xx	xx	xx	xx	
Wound Care		x	x	xx	xx	xx	xx	xx	xx	xx	xx	xx	xx	x
Ulcer History	х													
Ulcer Assessment	x	x	x	xx	xx	xx	xx	xx	xx	xx	xx	xx	xx	x
Ulcer Photography		x	x	x					v13					x
Ulcer Biopsy			x											
Ulcer Microbiome			v2											x
Dose Modification									v13					

^{*:} For women of childbearing potential only

xx: Twice per week assessment

a: If the subject had documented normal G6PD and metHb lab results, then no need to repeat

b: Only if no results available within 3 months

€: Screening and baseline can be combined into one visit

After the first three subjects have completed the study, if there are no significant side effects, especially significant changes in BP, patients will be offered the option of applying the second weekly dose of the cream at home, by themselves or by a home health nurse. Dose modification and ulcer photography for visit 13 can be done anytime between visit 11-15.

34

15. References Cited

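### On-treatment methemoglobin sampling and the start of home dosing are each stated in conflicting ways, and neither home-dosing rule is tied to the subject's own early blood-pressure checks

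*Combined protocol and SAP*

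**What the plan says.** **Methemoglobin on treatment.** Section 7.1 states: "The primary expected toxicity is low grade, asymptomatic methemoglobinemia". For that reason, it continues, "a blood sample for methemoglobin safety measurement will be obtained after the first application, then weekly". Section 5.3 says of visit 3 that "Methemoglobin will be obtained one hour ± 30 min after" cream application, and of weeks 2 to 10 that "A research methemoglobin level will be obtained every other week". The schedule of procedures (the table after Section 13) has a single MetHb row. Apart from screening, it is marked only at visit 3, week 5 and week 9. Section 7.2 discontinues the cream on any reading above 7.5%.

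**Home application.** Section 5.3 gives the condition as "After the first three subjects have completed the first application of the study drug" without significant side effects; then "patients will be offered the option of applying the second weekly dose of the cream at home". The schedule footnote makes the same offer on a different condition: "After the first three subjects have completed the study, if there are no significant side effects".

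**Blood pressure.** From visit 4, Section 5.3 requires a reading on arrival at the outpatient unit and another about 30 minutes after the cream. The later reading may be dropped on this condition: "If the blood pressure is stable after cream application for all visit 4, 5, 6". Section 7.2 has a dose skipped when a repeat check confirms systolic pressure of 80 mmHg or less and/or diastolic of 50 mmHg or less. The schedule marks vital signs twice in every treatment week.

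**The concern.** An asymptomatic rise in methemoglobin is found only by drawing blood, and the Section 7.2 stopping level can act only on a sample that exists. Staff who work from the schedule table, as site staff commonly do, would sample well below what Section 7.1 requires, and nothing in the table would show it. The table's gap from week 5 to week 9 also contains the mid-course dose review (visit 13, week 6), at which Section 5.4 can raise the dose by half.

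The two home-dosing conditions differ greatly in how much supervised experience precedes unsupervised use. The two sites named in Section 5.3 could apply different rules and each cite the protocol.

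Blood pressure is a stated question of the trial. Section 2.4.2 expects the placebo comparison to show whether the phase 1 fluctuations are intrinsic to these patients. At the 2% strength, diastolic pressure fell below 50 mmHg in 2 of 3 phase 1 subjects (Section 5.2, dose rationale). A home-dosing rule that takes no account of the subject's own early post-application readings fits poorly with that aim.

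**Working it through.** The protocol gives no figure of its own to reproduce. The check is a count under each text.

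**1. Methemoglobin samples per subject, full ten-week course.** Inputs: treatment weeks 1 to 10, two applications a week (Section 5.2); sampling rules as above. The table row was read against its 14 columns (screening, baseline, run-in, weeks 1 to 10, end of study). As an alignment check, the photography mark for visit 13 falls in the column for visits 13-14.

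| Source | Weeks sampled | Samples | Longest gap | Applications per gap (gap × 2) |
|---|---|---|---|---|
| Section 7.1 | 1, 2, …, 10 | 10 | 1 week | 2 |
| Section 5.3 | 1, 3, 5, 7, 9 or 1, 2, 4, 6, 8, 10 | 5 or 6 | 2 weeks | 4 |
| Schedule | 1, 5, 9 | 3 | 4 weeks | 8 |

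These are upper bounds, because the cream stops when the ulcer heals (Section 7.2). The shortfall of the table against Section 7.1 is 10 − 3 = 7 draws. That of Section 5.3 is 10 − 6 = 4 to 10 − 5 = 5.

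**2. Supervised experience before home dosing opens.**
- Section 5.3: 3 subjects × 1 application = 3.
- Schedule footnote, read as the end of treatment: 3 × 20 = 60 for ten-week courses, or 3 × 16 = 48 for eight-week completers.
- With blinded 1:1 allocation, about half of either total is active cream.
- Ten weeks is 70 / 30.44 = 2.3 months. At the planned 1 to 2 subjects a month (Section 5.2, sample size), about 2.3 to 4.6 subjects would start between the two points, assuming that treatment starts follow the enrolment rate.

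**3. Which blood-pressure checks can fall on a home dose.** The schedule puts visits 2w + 1 and 2w + 2 in week w, so the second weekly doses are visits 4, 6, …, 22, which is 10 of 20. Of visits 4, 5 and 6, only visit 5 is a first weekly dose. For visit 4, Section 5.3 separately tells the subject to come back for the second application. No such instruction covers visit 6. Section 5.3 heads its paragraph as weeks 2 to 10 and visits 4 to 22, while the schedule places visit 4 in week 1. If visit 4 opened week 2 instead, the affected visit numbers would shift, but at least one of the three would still be a second weekly dose.

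**The case against.** The best defence of the sampling text is that Section 5.3 describes a research level and Section 7.1 a safety level, so they may be separate series. That does not settle it, because the schedule's only MetHb row matches neither. It is also fair that weekly sampling satisfies all three statements, and that the later home-dosing condition satisfies both texts. A careful site can therefore comply with everything. That stands, and it makes the remedy a wording change. It does not tell a site working from the table that the table falls short.

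A reader might infer that the footnote's condition is itself unclear, since Section 5.2 keeps subjects on study for six months after treatment. The documents do not support this: Section 5.2 (measurement times), Section 5.3 and the schedule's final visit all tie the end of study to the last application.

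A reader might also infer that the checks at visits 4 and 6 will go unmade in nearly all subjects. That is too strong. The return instruction keeps visit 4 on site, and the schedule requires vital signs twice a week. The post-application check lapses only after stable readings at all three visits, so a subject without them continues to be checked. Home dosing is optional. Nor is the number affected capped at 50 − 3 = 47, because under Section 5.3 the third subject's own later doses also qualify. What remains is narrower: nothing keeps visit 6 on site, and nothing says how the 30-minute check or the dose-skip rule works for a home dose.

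Phase 1 is reassuring. Methemoglobin peaked at 4.1% in one subject and did not change in the other 17 (Section 5.2), with no accumulation over four weeks. The low diastolic readings resolved within an hour, some preceded the cream, and Section 2.4 calls the link unclear. This limits the likely harm, although the course is now ten weeks.

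**Conclusion.** The point holds. Two safety-conduct rules conflict in the current text with no order of precedence: methemoglobin sampling (10, 5 to 6, or 3 draws per full course) and the start of home dosing (3 against 48 to 60 supervised applications). Both should be corrected. The missing link between home dosing and the subject's own checks at visits 4, 5 and 6 is a smaller gap and a cheap improvement; it is certain only for visit 6.

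The counts assume a full course, the schedule's visit numbering, and table columns that survived text extraction intact. A reader might go on to infer lost power, inflated type I error or a biased comparison of arms. The documents give no basis for that: the rules are the same in both blinded arms, and no effect on the adverse-event comparison has been quantified. This is a matter of patient protection and consistent conduct, probably with modest consequences.

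**What to change.** 1. **Methemoglobin.** Keep Section 7.1. Change the every-other-week sentence in Section 5.3 and the schedule's MetHb row to a sample after the first application and then weekly. This means up to 7 more draws per subject than the table and 4 to 5 more than Section 5.3. Section 7.1 already requires all of them, and they fit the weekly clinic visit that home dosing leaves in place.
2. **Home dosing.** State one condition in Section 5.3 and the schedule footnote, preferably that three subjects have completed the ten-week treatment. Home dosing then opens about ten weeks later. The first three subjects and roughly 2 to 5 later starters keep twice-weekly visits for longer, at most 10 extra visits each.
3. **Individual condition.** Add that no subject starts home dosing until on-site post-application blood pressure has been stable at visits 4, 5 and 6. The cost is one to two extra clinic visits per home-dosing subject (visit 6, and visit 4 if it would otherwise go home), leaving 10 − 2 = 8 of 20 doses available for home use. If three subjects have already met the trial-level condition, which the documents do not say, this is the home-dosing change that still acts.

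No extra patients are needed.

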7.2 Stopping Rules

The study medication will be stopped if the subject experiences healing of the ulcer.

Subjects will be removed from therapy should one or more of the following occur:

- If any methemoglobin reading is >7.5%, the research study cream will be discontinued.
- Investigator or patient considers discontinuation of the study to be in the patient's best interest.
- Clinically significant hypotension (decrease in the systolic BP >20mmHg from the baseline systolic BP and of 10mmHg from the baseline diastolic BP application, and symptomatic dizziness, tachycardia, or hypoxia as per the judgment of the PI).
 - A dose will be skipped if the subject has a systolic blood pressure of ≤80mmHg and/or a diastolic blood pressure of ≤50mmHg, once the blood pressure has been checked with a repeat blood pressure check. If three doses are skipped in a row for this reason, the subject will be removed from therapy.
- Sustained pulse oxygen saturation below 85% for >15 minutes while on supplemental oxygen (up to 4L by NC).

- Increased ulcer pain requiring increased opioid use by 50%.
- Development of osteomyelitis or other systemic infection while on therapy.
- Lack of compliance, as measured by missing more than two sequential cream applications and/or at the PI's discretion.

Rules for Stopping the Study:

- Occurrence of severe toxicities:
 - Three subjects requiring sodium nitrite cream discontinuation
 - Death while on protocol, if it is attributable to the sodium nitrite cream

8. **Analysis of the Study**

We will first review and summarize data using descriptive summaries and graphical analyses to ensure recorded values are within appropriate ranges, in order to check for outliers and abnormal values. We will explore the success of randomization by comparing groups on potential confounding variables, and will include variables that are not equally distributed between groups in multivariable models. For primary analyses, we will adhere to the intent-totreat analysis principle that assigns groups as randomized as opposed to actually treated. For sensitivity analyses, we will conduct as-treated analysis and use incomplete data as well after imputation of missing data due to early dropouts; imputation methods such as last-observationcarried-forward or MCMC will be conducted and results from thereof will be compared.

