During the abovementioned phase 1 trial of topical sodium nitrite, we observed no SAE's. We documented a grade 1 decrease in diastolic blood pressure below 50 mmHg, judged as possibly related to study drug 16 times in 4 participants. Of the four participants, two enrolled in Cohort 4, the highest concentration of the drug (2.0% sodium nitrite cream) and the other two enrolled into Cohort 3.a (1.8% sodium nitrite cream). The participants had fluctuating diastolic blood pressure measurements that occasionally reached below 50 mmHg even **before study cream application**; therefore, the association with study cream application is unclear. All events resolved spontaneously within an hour (i.e., at the next BP check).

15

PI: [name] Version 5

Experiments in rats showed that methemoglobin levels peaked at 45-50 min after application of 30 g/L sodium nitrite solutions on abraded skin³². Percutaneous absorption of a solution differs from the absorption rate from Aquaphor (the vehicle in our current preparation) and it seems to be slower than that from solution. There was no evidence of accumulation either, as predicted by our pharmacokinetic models^{34,35}.

In the proposed phase 2 trial we plan to answer this toxicity question, since we will be treating patients blindly with a placebo preparation and we will be able to ascertain whether the fluctuations in BP are intrinsic to this patient population, their frequent use of opioids, and/or chronic wide pulse pressure.

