5.4 Dose Adjustment

Sodium nitrite dose will be modified according to this scheme:

- a) If a subject's ulcer surface decreases by more than 50% of the original area, as measured after 10 applications, a 50% reduction in the dose of sodium nitrite willtake effect for the remaining applications.
- b) If a subject's ulcer(s) increase by 50% of the original area, as measured after10 applications, a 50% increase in the dose of sodium nitrite will take effect for the remaining applications.

Dose-limiting toxicities are defined as:

- Severe stinging pain or burning sensation, requiring a 50% increase in opioiduse.
- •Peripheral edema causing significant discomfort by patient subjective report.
- Clinically significant hypotension or symptomatic dizziness, tachycardia, or hypoxia as per the judgment of the PI
- •Methemoglobinemia >7%

In the event that a subject experiences dose limiting toxicity, he/she will discontinue participation in the protocol.

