PI: [name] Version 5 62/077,622, filed on November 10, 2014, entitled "TOPICAL SODIUM NITRITE FORMULATION," and PCT Patent Application No. PCT/US2015/060015, filed on November 10, 2015, entitled "TOPICAL SODIUM NITRITE FORMULATION," has six inventors: [name], [name], [name], [name], [name], and [name], who were all NIH employees at the time of invention.

- Or. [name] is presently employed on the faculty of the University of Pittsburgh.
- oDr. [name] is presently employed on the faculty of the Albert Einstein College of Medicine.

12 Adverse Events Reporting

The Principal Investigator (or a physician member of the research team) and the study coordinator will assess each participant for any new or continuing adverse events. An adverse event is defined as any untoward medical occurrence in a subject of a clinical investigation that involves the administration of a pharmaceutical product. The event need not to have a causal relationship with the treatment. This includes any events that are not seen at baseline or, if present at baseline, have worsened in severity. These adverse events will only be collected during study treatment time. The severity and drug relationship will be determined, and any management required will be recorded. The investigator will review the clinical laboratory test results in a timely fashion. Only those results qualifying as adverse events, as defined above, will be recorded as an adverse event.

Table 2. Expected Adverse Events Possibly Related to Study Drug						
Severe stinging and burning sensation, requiring an increase in narcotic use.						
Peripheral vasodilation with hypotension (BP below 85/50, or symptomatic						
dizziness, tachycardia, or hypoxia as per the judgment of the PI)						
Methemoglobinemia >7.5%						

Acute chest syndrome Angioedema Angioedema Aplastic crisis Aplastic crisis/anemia Aplastic crisis/anemia Appendicitis Bone Infarction Cardiomegaly Cerebrovascular accident Cholecystitis, hepatic sequestration Cranial nerve palsy Decreased kidney function Decreased lung function Pever Renal Insufficiency/albuminuria Headache Hematuria Hematuria Reticulocytosis (10%-20%) Hemiplegia Hemolysis Hepatosplenomegaly Hyperplastic bone marrow Hyposthenuria Increase Jaundice Metabolic acidosis	Table 3. Expected Adverse Events Re	elated to Sickle Cell Disease

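### Sections 5.4 and 7.2 set conflicting hypotension criteria for ending treatment: one joins pressure fall and symptom with 'or', the other with 'and'

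*Combined protocol and SAP*

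**What the plan says.** **Ending treatment.** Section 5.4 lists dose-limiting toxicities. One item is "Clinically significant hypotension or symptomatic dizziness, tachycardia, or hypoxia as per the judgment of the PI", with no pressure value attached. The consequence is stated: "In the event that a subject experiences dose limiting toxicity, he/she will discontinue participation in the protocol".

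The subject-level list in Section 7.2 opens with "Subjects will be removed from therapy should one or more of the following occur". Its hypotension item is defined as a "decrease in the systolic BP >20mmHg from the baseline systolic BP and of 10mmHg from the baseline diastolic BP application, and symptomatic dizziness", with tachycardia or hypoxia as alternative symptoms and the investigator judging. This is the only numeric definition of clinically significant hypotension in the protocol. Section 7.2 also has a separate dose-skip rule (confirmed systolic at or below 80 mmHg and/or diastolic at or below 50 mmHg). Three skips in a row lead to removal.

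**Discharge after application.** In Section 5.3 (Week 1/Visit 3) the test is "If no significant decrease in MAP pressure from baseline is detected", explained in brackets as hypotension or a symptom. In Section 7.1 it is "If no decrease in systolic blood pressure is detected", with a pointer to Section 7.1 for the meaning of clinically significant hypotension.

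**Expected events.** Table 2 in Section 12 lists "Peripheral vasodilation with hypotension (BP below 85/50, or symptomatic" dizziness, tachycardia or hypoxia.

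**What depends on these rules.** Section 5.2 lets the medical monitor request unblinding when a dose-limiting toxicity occurs. Section 7.2 stops the study for severe toxicity once three subjects have had to come off the nitrite cream.

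**The concern.** Sections 5.4 and 7.2 do the same job: each says when an individual subject must stop. One joins the pressure fall and the symptom with 'or', the other with 'and', so site staff can follow the protocol faithfully and reach opposite answers about the same subject. Two centres enrol, so the reading could also differ by site.

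Three things are at stake. The first is the safety of the individual subject. The second is the blind, because a dose-limiting toxicity is a ground for requesting unblinding, while meeting or missing the 7.2 criterion is not mentioned as one. The third is the study-level stop, which counts discontinuations. Blood pressure is also the toxicity the sponsor most wants clarified. Section 2.4.2 says of the blood-pressure fluctuations seen in Phase 1: "In the proposed phase 2 trial we plan to answer this toxicity question".

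**Working it through.** The plan gives no figure to reproduce. The check sets the rules side by side and applies them to illustrative events.

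**Rules as logic.** Let S be the systolic fall, D the diastolic fall, and Y a qualifying symptom in the investigator's judgment.

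- Section 7.2 hypotension criterion: S > 20 and D ≥ 10 and Y. (The text gives a diastolic fall of 10; I read it as at least 10.)
- Section 5.4: H or Y, where H is clinically significant hypotension, undefined in that section.

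**Does borrowing the 7.2 definition help?** Put H = (S > 20 and D ≥ 10 and Y) into 5.4. The rule becomes (S > 20 and D ≥ 10 and Y) or Y, which reduces to Y. A symptom alone still suffices, so the conflict remains. Every event that meets 7.2 contains a symptom and so already meets 5.4. If both rules apply together, the pressure thresholds in 7.2 never decide anything.

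**Illustrative events** (assumed pressures; the symptom is taken as qualifying under both sections):

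| Event | S | D | Section 5.4 | Section 7.2 hypotension criterion |
|---|---|---|---|---|
| 120/70 to 114/68, dizziness | 120 − 114 = 6 | 70 − 68 = 2 | Met: participation ends | Not met |
| 120/70 to 90/65, dizziness | 120 − 90 = 30 | 70 − 65 = 5 | Met: participation ends | Not met (D below 10) |
| 120/70 to 95/58, dizziness | 120 − 95 = 25 | 70 − 58 = 12 | Met: participation ends | Met: removed from therapy |

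The first two events show the conflict. In the third the sections agree that treatment ends, although one speaks of leaving the protocol and the other of leaving therapy.

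**Discharge.** Take MAP = diastolic + (systolic − diastolic)/3. For 120/70, MAP = 70 + 50/3 = 86.7. For 114/68, MAP = 68 + 46/3 = 83.3. The change is −3.3 mmHg. The literal systolic test in 7.1 is failed, because systolic pressure fell by 6. The MAP test in 5.3 asks whether the fall is significant and gives no value.

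**Sensitivity of the study stop.** With 50 randomised 1:1, about 25 receive nitrite. For a per-subject discontinuation rate p, which the documents do not give,

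P(at least 3 of 25) = 1 − Σ C(25,k) p^k (1 − p)^(25 − k), summed over k = 0, 1, 2.

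At p = 10%: 1 − (0.0718 + 0.1994 + 0.2659) = 0.463.

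| Assumed p | P(at least 3 of 25) |
|---|---|
| 2% | 1.3% |
| 5% | 12.7% |
| 10% | 46.3% |
| 15% | 74.6% |
| 20% | 90.2% |

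If the choice of rule moves p, the chance of stopping moves steeply with it. The table does not show by how much the wording would move p.

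**The case against.** The best defence is that the lists are cumulative. Section 7.2 removes subjects who meet any of its items and does not say that others must continue, so a symptom-only event ends participation through 5.4 whatever 7.2 says. Section 7.2 also lets the investigator stop treatment in the patient's best interest, and the study-stop count is not confined to the hypotension item. All of this is a fair reading, but the protocol nowhere states it, it leaves the 7.2 pressure thresholds without effect, and investigator discretion is case-by-case judgment that does not reconcile two written rules.

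Several stronger inferences are tempting, and here the defence is right:

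- *Four rival definitions.* Only 7.2 defines the term numerically. Sections 5.3 and 5.4 use it without a value, and 7.1 refers elsewhere. A symptomless fall of 25/12 mmHg is limiting under 5.4 only if 5.4 borrows the pressure part of the definition without the symptom.
- *Section 7.1 is circular.* The contents list numbers Stopping Rules as 7.1, while the body numbers it 7.2. The pointer is most likely a stale section number.
- *A symptomless diastolic reading just below 50 is caught by Table 2 alone.* It also lies in the 7.2 dose-skip range.
- *The primary adverse-event count depends on which section is followed.* Section 12 records any untoward occurrence and Table 2 only lists expected events. Section 8.1.1 compares total adverse-event counts and plans no separate blood-pressure result.
- *Phase 1 shows that the conflict will arise often.* Diastolic readings below 50 in 2 of 3 subjects at 2% bear on the dose-skip and Table 2 levels, not on 5.4 against 7.2. Some of those participants were below 50 before application, and the events resolved within an hour.

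Dose-skip, discharge and expected-event thresholds may properly differ, since they serve different purposes.

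**Conclusion.** The concern holds for Section 5.4 against Section 7.2. As written, a symptom without the full pressure fall ends participation under one rule and does not meet the hypotension criterion of the other, and no order of precedence is given. The mismatch in discharge wording and the outdated cross-reference are secondary but real.

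The conclusion rests on the wording and on no assumed rate. Its practical size is unknown: the documents do not give the frequency of symptom-only events, and the stopping probabilities above only show how sensitive a three-subject rule is. The consequences supported by the text are for who stops treatment, when unblinding may be requested, and possibly the study-stop count. An effect on the primary adverse-event comparison is not shown. The correction should be made because the rules concern subject safety and the remedy is simple.

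**What to change.** 1. Reconcile 5.4 and 7.2 so that the same event has the same consequence, or state which rule governs. Say also whether leaving the protocol and leaving therapy mean the same thing.
2. Align the discharge tests in 5.3 and 7.1, or explain why they differ.
3. Correct the pointer in 7.1 to the section that now holds the definition.
4. If the dose-skip level in 7.2 and the Table 2 level are meant to differ from the removal criterion, label each as a threshold with its own purpose.

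The sponsor chooses the clinical values; this review takes no view on them. The cost is a protocol amendment to wording, which Section 13 says the IRB must approve. No new measurements are needed, because the rules use vital signs and symptoms that the protocol already monitors.
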